#### *Success Criteria and Alternative Plan*

The project will be considered successful when all procedures of 6 volunteers are completed each week. Since the researchers will carry out all measurements if the operation dates of the volunteers change or there is disruption due to the work intensity/excuse of the researcher, the disrupted time will be compensated by performing the procedures of more than 6 volunteers per week.

#### **Statistical Analysis Plan**

The Shapiro-Wilk test will be used to check the normal distribution of the numerical data, and the kurtosis and skewness coefficients will also be examined. Variance homogeneity will be analyzed using Levene's test. Independent samples t-test, Welch test, or Mann-Whitney U test will compare the groups depending on the data distribution. Depending on the expected value rule, categorical variables will be analyzed using Pearson chi-square, Fisher's exact, or Fisher-Freeman-Halton tests. A comparison of the values measured at different periods during the operation will be performed using repeated measures ANOVA. Pearson correlation or Spearman's rho will be used in correlation analyses depending on the data distribution. Descriptive statistics will be given as mean±standard deviation or median, quartiles, and minimum-maximum values depending on the data distribution, and categorical variables will

be summarized as numbers and percentages. Statistical analyses will be performed using SPSS v.22 (IBM Corp. Released 2013. IBM SPSS Statistics for Windows, Version 22.0. Armonk, NY: IBM Corp.) package program, and the significance level will be taken as 0.05.

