In our study, two groups will be formed: low flow group and high flow group. Vitamin D, albumin, CRP, TAS, and TOS values will be checked from all patients before and during the operation. During the operation, 1 L/min fresh gas flow will be given to the low-flow group, 4 L/min fresh gas flow will be given to the high-flow group, and the processed EEG values of all patients will be monitored, and the same depth of anesthesia will be ensured. Albumin, CRP, TAS, and TOS values from the postoperative blood samples of the patients taken to the ward after the operation will be rechecked, and these values will be compared with the previous values.

Our study will compare the changes in total oxidant and total antioxidant systems in general anesthesia methods applied with 1 lt/min and 4 lt/min flows. Studies show patient-based advantages of low-flow anesthesia, such as respiratory functions and inflammatory response in the postoperative period. However, very few studies show its effects on oxidative stress, and a comprehensive study evaluating total oxidant/antioxidant systems was not found in our literature review. Therefore, our study will contribute to the literature.

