### *Exclusion criteria:*

ASA III and above patients,

Patients for whom an Intensive Care Unit (ICU) indication is foreseen

Chronic obstructive pulmonary disease,

A personal or family history of malignant hyperthermia,

Morbid obesity,

Alcohol or drug addiction,

History of liver or kidney disease,

With coronary artery disease or heart failure,

Significant anemia or hemoglobinopathy,

Hypotension, hypovolemia, sepsis.

After the patients who meet the specified criteria are informed about the study, volunteers who agree to participate and sign an informed consent will be included. Vitamin D, albumin, CRP, Total Antioxidant Status (TAS), and Total Oxidant Status (TOS) levels will be measured in the blood samples obtained from all volunteers' preoperative routine blood samples. After all volunteers are admitted to the operation room, they will be monitored with electrocardiography, pulse oximetry, non-invasive blood pressure, end-tidal carbon dioxide, temperature probe, and processed electroencephalogram- -bispectral index (BIS) without any medication. Baseline peak heart rate (HR), peripheral oxygen saturation (SpO2), systolic (SBP) and diastolic blood pressure (DBP), end-tidal carbon dioxide (ETCO2), body temperature, and BIS will be recorded. All measurements will be repeated and recorded at 5-minute intervals during the operation.

Volunteers will be divided into low-flow group (D) and high-flow group (Y). D group will receive 1 L/min fresh gas flow, and Y group will receive 4 L/min fresh gas flow. Processed EEG values of all patients will be monitored during the operation and ensured they are at the same depth of anesthesia. Albumin, CRP, TAS, and TOS values will be rechecked in the postoperative blood samples of the patients during and after the operation and compared with the previous values.

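### The SAP names no baseline-adjusted comparison of the flow groups, nor whether values or changes are tested; if allocation is random, ANCOVA on preoperative TAS and TOS would usually be more precise

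*Combined protocol and SAP*

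**What the plan says.** The Introduction states the aim as a comparison of changes: "Our study will compare the changes in total oxidant and total antioxidant systems in general anesthesia methods". The preoperative sample is described in the text below the exclusion criteria, where TAS and "Total Oxidant Status (TOS) levels will be measured in the blood samples obtained from all" volunteers. The same section says that albumin, CRP, TAS and TOS will be "rechecked in the postoperative blood samples of the patients during and after the operation and compared with the previous values". The Introduction also describes a ward sample: "Albumin, CRP, TAS, and TOS values from the postoperative blood samples of the patients taken to the ward after the operation will be rechecked".

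The Statistical Analysis Plan then gives the between-group method: "Independent samples t-test, Welch test, or Mann-Whitney U test will compare the groups depending on the data distribution". It names no analysed variable and no covariate. Its only longitudinal method is worded for the intraoperative period: "A comparison of the values measured at different periods during the operation will be performed using repeated measures ANOVA". That sentence names no marker, no preoperative sample and no group-by-time term.

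On allocation, the available text says only: "Volunteers will be divided into low-flow group (D) and high-flow group (Y". Parts of the document were not available for this review, so nothing here claims that the plan lacks an allocation method, a sample size or a named primary outcome.

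**The concern.** The baseline of each outcome marker is taken in everyone, before exposure to the assigned flow. The SAP does not say how it enters the group comparison. Two readings are open: an unadjusted test of postoperative values, which ignores the baseline, or the same test on change scores, which subtracts it with a fixed coefficient of 1. ANCOVA estimates that coefficient from the data and so usually has a smaller standard error than either.

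Two things are at stake. One is power for the trial's main question, at no cost in patients or samples. The other is that, as written, the analysed variable could be chosen after the data have been seen.

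**Working it through.** **Inputs from the documents.** The significance level: "the significance level will be taken as 0.05". Sidedness is not stated; two-sided is assumed. The available text gives no sample size, power, SD or correlation, so there is no figure of the plan's own to reproduce.

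**Assumed inputs.** Random allocation; equal arms and equal slopes; r = correlation of preoperative with postoperative value, taken as 0.3, 0.5, 0.7; k = SD_pre/SD_post, taken as 0.5, 1, 1.5; N = total sample size, 20 to 100. Both r and k may differ between markers.

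**Large-sample variance of the group difference, relative to the postoperative value alone**
- Change score: 1 + k² − 2rk
- ANCOVA: 1 − r²

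At r = 0.5, k = 1: change score 1 + 1 − 1 = 1.00; ANCOVA 1 − 0.25 = 0.75.

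| | r = 0.3 | r = 0.5 | r = 0.7 |
|---|---|---|---|
| ANCOVA / postoperative value (any k) | 0.91 | 0.75 | 0.51 |
| ANCOVA / change, k = 0.5 | 0.96 | 1.00 | 0.93 |
| ANCOVA / change, k = 1 | 0.65 | 0.75 | 0.85 |
| ANCOVA / change, k = 1.5 | 0.39 | 0.43 | 0.44 |

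The last three rows are (1 − r²)/(1 + k² − 2rk). This equals 1 exactly when k = r, as at r = k = 0.5.

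**Power.** Where the comparator has 80% power, ANCOVA has Φ((1.960 + 0.8416)/√ratio − 1.960).
- Against the postoperative value: 83.6%, 89.9%, 97.5% at r = 0.3, 0.5, 0.7.
- Against change scores with k = 1: 93.5%, 89.9%, 86.0%.

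**Small-sample cost.** With a normal covariate, the ratio against the postoperative value becomes (1 − r²)(N − 3)/(N − 4), with N − 3 in place of N − 2 degrees of freedom. Variance breaks even at |r| = 1/√(N − 3). Power from the noncentral t distribution, where the postoperative comparison has 80%:

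| N | break-even \|r\| | ANCOVA power at r = 0 |
|---|---|---|
| 100 | 0.10 | 79.6% |
| 60 | 0.13 | 79.3% |
| 40 | 0.16 | 78.9% |
| 30 | 0.19 | 78.4% |
| 20 | 0.24 | 77.3% |

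At N = 60 and r = 0.3, 0.5, 0.7, ANCOVA has 82.9%, 89.4% and 97.3%.

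**Simulation check.** With 30 per arm, r = 0.5, k = 1 and 10,000 runs, the empirical standard errors were 0.258 (postoperative value), 0.256 (change) and 0.224 (ANCOVA). The variance ratio (0.2241/0.2582)² = 0.75 agrees with the formula.

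**The repeated measures ANOVA.** With one preoperative and one postoperative value, its group-by-time test would be the change-score t-test. The documents describe samples before, during and after the operation; with three time points that equivalence does not hold. The analysis would still not be an ANCOVA, and the SAP sentence does not say that it covers TAS or TOS.

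**The case against.** **The baseline may already be used.** A reader might infer that the SAP ignores the preoperative values. The documents do not support that. The Introduction speaks of comparing changes, and both sections that describe the later samples speak of comparison with previous values. A t-test or Mann-Whitney test on changes would fit every sentence. What stands is narrower: the SAP does not say which variable is tested and names no adjusted model.

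**The gain is conditional.** This is correct. If allocation is not random, ANCOVA and change scores can target different quantities, and precision does not decide between them. Even under randomisation, a model without interaction is not always the more precise with unequal arms and unequal slopes. Take 3:1 allocation, unit SDs, and slopes of 0.8 in the larger arm and 0 in the smaller. The pooled slope is 0.75 × 0.8 = 0.6. The adjusted variances are 1 − 2(0.6)(0.8) + 0.36 = 0.40 and 1 + 0.36 = 1.36. The ratio to the unadjusted variance is (0.40/0.75 + 1.36/0.25)/(1/0.75 + 1/0.25) = 5.97/5.33 = 1.12. That case is deliberately unfavourable, but the available text gives no allocation ratio, so the condition must be stated.

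**The change may not be free.** The small loss in the table applies to adding the covariate alone. Sharing the 0.05 level between TAS and TOS would be a different change with a larger price. At Holm's first step of 0.025 with N = 60, a marker that had 80% power unadjusted at 0.05 would have 69.8% with ANCOVA at r = 0 and 74.3% at r = 0.3. These are lower bounds per marker, since Holm tests the second at 0.05 once the first is rejected. Multiplicity is therefore kept out of this point.

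**Skewed markers.** The SAP's Mann-Whitney option would be lost unless a substitute is fixed. This stands and is covered in the fix. The gain over Mann-Whitney itself was not calculated.

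**Conclusion.** The point holds as an improvement in precision. The SAP leaves the analysed variable open and prespecifies no baseline-adjusted group comparison, while the necessary baseline is already collected. Under random allocation, with equal arms or equal slopes, ANCOVA would usually be more precise than either reading of the plan. Over the assumed range of r, variance falls by 9% to 49% against postoperative values, and by 35% to 15% against change scores with equal SDs. Against change scores the gain depends on the SD ratio and can be nil.

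The actual gain cannot be fixed from the documents, because r, k and N are all assumed here. It would also go too far to call the planned tests invalid: under randomisation they are valid, only generally less precise.

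**What to change.** In the Statistical Analysis Plan, state that the between-group comparison of TAS and of TOS is an ANCOVA of the postoperative value on group, with the same marker's preoperative value as covariate. Do not use the intraoperative value as covariate, because it is taken after exposure to the assigned flow has begun. Report the adjusted difference with its 95% confidence interval, and state that the preference for ANCOVA assumes random allocation.

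Fix the scale of each marker in advance, or a rank-based version for skewed markers, instead of choosing after inspecting the distribution. A rank-based version does not give an adjusted difference on the marker's own scale, so the reported estimate must then be specified too.

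The cost is SAP wording and one degree of freedom per model, with no extra patients or samples. If the baseline proves uninformative, the loss from 80% power is about 1 percentage point or less at N of 40 or more, and 2.7 points at N = 20. The choice of lead outcomes and any sharing of the 0.05 level are separate decisions with their own power cost and are not part of this change.

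### The group test is picked from the observed data, so each blood marker's target (means or rank order) is not fixed in advance, and the preoperative value already collected goes unused.

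*Combined protocol and SAP*

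**What the plan says.** The Statistical Analysis Plan sets out three checks on the trial data before the groups are compared:

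- Normality: "The Shapiro-Wilk test will be used to check the normal distribution of the numerical data".
- Shape: "the kurtosis and skewness coefficients will also be examined".
- Spread: "Variance homogeneity will be analyzed using Levene's test".

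It then says "Independent samples t-test, Welch test, or Mann-Whitney U test will compare the groups depending on the data distribution". The reported summary switches on the same basis: "Descriptive statistics will be given as mean±standard deviation or median, quartiles, and minimum-maximum values depending on the data distribution". For error control it says only that "the significance level will be taken as 0.05".

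The section gives no cut-off for any check. It does not say whether normality is judged per group or pooled, or what happens when Shapiro-Wilk and the skewness and kurtosis coefficients disagree. No test or target quantity is fixed for any marker or time.

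The text under the exclusion criteria has albumin, CRP, TAS and TOS measured before surgery in every volunteer, and then "Albumin, CRP, TAS, and TOS values will be rechecked in the postoperative blood samples of the patients during and after the operation", for comparison with the preceding values. A baseline therefore exists for all four markers.

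**The concern.** The t and Welch tests compare means. Mann-Whitney compares rank order, that is, whether a patient in one group tends to have a higher value than a patient in the other. If the sample decides which is used, the plan does not say what is being estimated until the data are seen. TAS might be compared on means and TOS on ranks, or one marker on means during surgery and on ranks afterwards, with no scientific reason for the difference. The unruled look at skewness and kurtosis leaves the analyst further discretion.

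Two consequences follow. A significant Mann-Whitney result can arise when the means are equal but the spreads differ, and a reader may take it as a difference in average level. Also, all three tests use the later values alone, although each patient's own preoperative value is available and would usually sharpen the comparison.

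**Working it through.** **Inputs.** From the documents: significance level 0.05, two groups, four markers with a preoperative and later values. Everything else is assumed, because the text available for review gives no sample size, SD, distribution shape, cut-off, allocation ratio or sidedness. Part of the protocol was not available, so the missing sample size is not counted against the plan. The plan has no figure of its own to reproduce beyond the 5% level.

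**Rule simulated.** Shapiro-Wilk p<0.05 in either group leads to Mann-Whitney. Otherwise Levene p<0.05 leads to Welch. Otherwise the pooled t-test is used. All tests are two-sided at 0.05. Skewness and kurtosis were not modelled, as they have no rule.

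**Step 1: how often the target changes.** With mild skew (lognormal, log-SD 0.25, same in both groups), Mann-Whitney is selected in about 34%, 48% and 60% of trials at 20, 30 and 40 per group. If p is that chance and four markers were independent, the chance that they do not all land on the same kind of test is 1 − p⁴ − (1 − p)⁴:

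- p = 0.34: 1 − 0.013 − 0.190 = 0.80
- p = 0.48: 1 − 0.053 − 0.073 = 0.87
- p = 0.60: 1 − 0.130 − 0.026 = 0.84

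Simulations with correlated markers gave 66-87%.

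**Step 2: error rate for equal means, where it holds.** At 10,000 trials per setting (standard error about 0.2 points):

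- Same distribution in both groups: 4.4-5.6%.
- Normal data, equal sizes, SD ratio 1.5 or 2: 5.0-5.8%.
- Normal data, unequal sizes (40/20, 20/40, 33/27), SD ratio 1.5 or 2: 4.1-6.6%. The rate is above 5% when the smaller group is the more variable and below 5% when it is the less variable.

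**Step 3: where it does not hold.** For a lognormal variable with mean 1 and log-SD s, the median is exp(−s²/2). For two such groups, P(Y > X) = Φ[(s_X² − s_Y²)/2 ÷ √(s_X² + s_Y²)].

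- 0.3 vs 0.5: medians 0.956 and 0.882; P(Y > X) = Φ(−0.08/0.583) = 0.445.
- 0.5 vs 0.9: medians 0.882 and 0.667; P(Y > X) = Φ(−0.28/1.030) = 0.393.

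The means are equal, but rank order is not (0.5 would be no difference). Rejection rates over 20-40 per group, rising with group size:

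| Log-SD | Plan's rule | Welch, raw scale | Welch-type comparison, log scale |
|---|---|---|---|
| 0.3 vs 0.5 | about 9-14% | about 5-6% | about 8-14% |
| 0.5 vs 0.9 | about 22-37% | about 7% | about 23-38% |

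Separate runs differ by one or two points. The last column matters for the fix: a log-scale analysis also rejects equal raw means here, because it compares geometric means.

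**Step 4: the baseline.** With n per group, effect δ in SD units and baseline correlation ρ, power ≈ Φ[δ√(n/2)/√(1 − ρ²) − 1.96]. For n = 40 and δ = 0.5, δ√(n/2) = 0.5 × √20 = 2.236.

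| ρ | Argument before subtracting 1.96 | Approximate power | Simulated power |
|---|---|---|---|
| No adjustment | 2.236 | 61% | 58-60% (plan's rule) |
| 0.3 | 2.344 | 65% | about 62% |
| 0.5 | 2.582 | 73% | about 70% |
| 0.7 | 3.131 | 88% | about 85% |

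The simulated values for adjustment use a log-scale model with HC3 standard errors. They sit a few points below the approximation, which treats the SD as known. A fixed Welch test without baseline gives about 58%, the same as the rule.

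**The case against.** The strongest reply is that the rule does little harm to the type I error. A reader might infer from the pretesting that the 5% level fails whenever the groups differ in spread. That is not supported: with normal data the rate stays near 5%, and with identical distributions it does so whatever the shape. Material excess needs skew and unequal spread together, and nothing in the documents shows that these markers are skewed or that gas flow changes their spread. Even then, a Mann-Whitney rejection is not a false positive for the hypothesis of equal distributions. This stands. It also shows where the real gap is, since the plan never says which hypothesis it means to test.

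A reader might also blame the power loss on the pretests. That is wrong too: a fixed Welch test has the same power, and the gain comes wholly from adding the baseline.

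A third inference would be that results on different scales cannot support one conclusion about oxidant balance. No formal combination of markers is planned, and the markers have different units anyway, so this goes beyond the text.

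Finally, the protocol says that later values will be compared with preceding ones, and the Statistical Analysis Plan includes a repeated measures ANOVA. The baseline is therefore not wholly ignored. However, that ANOVA is described for measurements at different times during the operation. It is not said to cover the blood markers or to give a baseline-adjusted comparison between groups.

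**Conclusion.** The concern holds in a limited form. The target of the group comparison is left to the data, with an unruled shape check on top, so it can differ between markers and times by chance. The group tests named do not use the preoperative value.

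The error-rate consequence is conditional. It is roughly nil with identical distributions or with normal data and equal group sizes. With skew and unequal spread together, equal means are rejected in about 9-14% to 22-37% of trials, because the hypothesis changes. The baseline consequence is separate: about 2 to 4 points of power at a correlation of 0.3, 10 to 12 at 0.5 and 25 to 27 at 0.7.

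All these sizes rest on assumed group sizes (20-40, or 40 for power), lognormal shapes, cut-offs of 0.05, a 0.5 SD effect and assumed correlations. They show a range and do not predict this trial's results. The defect does not invalidate the trial, but the plan should be changed.

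**What to change.** Replace the data-driven choice of test in the Statistical Analysis Plan with the following, settled before the data are seen:

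1. For each blood marker, name the target and scale. Use the raw scale if a difference in means is wanted. Use the log scale if a ratio of geometric means is wanted, and state that this does not test equal raw means.
2. Compare the groups with one model at each planned sampling time: the later value on group plus the patient's own preoperative value, with HC3 standard errors. Report the estimate and its 95% confidence interval.
3. Where no baseline exists, use Welch's test on the fixed scale.
4. Use Shapiro-Wilk, skewness, kurtosis and Levene only as diagnostics on residuals. Keep Mann-Whitney as a labelled sensitivity analysis.

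This changes wording only and needs no new samples. The costs are that the scale must be chosen without sight of the data, and that the gain in power is small if the baseline correlation turns out low.

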## **Material and Methods**

### *Inclusion criteria:*

Patients older than 18 years and younger than 60 years to be operated under general anesthesia

Patients in the I and II risk groups, according to the American Society of Anesthesiologists (ASA) classification

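### For the 5-minute monitoring series, a mixed model with a group-by-time term would fit better than repeated measures ANOVA, which keeps only complete series and, as written, does not compare the two flow courses

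*Combined protocol and SAP*

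**What the plan says.** The procedures text in Material and Methods, which follows the exclusion criteria, lists seven monitored variables at baseline: HR, SpO2, SBP, DBP, ETCO2, temperature and BIS. It then says: "All measurements will be repeated and recorded at 5-minute intervals during the operation". The inclusion criteria admit "Patients older than 18 years and younger than 60 years to be operated under general anesthesia", with no limit on the type or length of operation. The same procedures text says of depth of anesthesia: "Processed EEG values of all patients will be monitored during the operation and ensured they are at the same depth of anesthesia".

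The Statistical Analysis Plan has one sentence on values over time: "A comparison of the values measured at different periods during the operation will be performed using repeated measures ANOVA". Group comparisons are in a separate sentence: "Independent samples t-test, Welch test, or Mann-Whitney U test will compare the groups depending on the data distribution".

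The available text gives no common last reading, no list of analysed times, no group-by-time term and no rule for series of unequal length. A part of Material and Methods between the procedures and the success criteria was not available to this review. It may settle some of this.

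**The concern.** Each patient's series is as long as that patient's operation, while repeated measures ANOVA needs a value at every analysed time. Applied to the full series, it drops patients with shorter operations. Cut to the shortest operation, it discards later readings. If a few times are selected, less is lost, but the available text names none. The choice decides which patients or readings count, and it could be made after the data are seen.

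The sentence also describes a comparison over time, not a comparison of the two flows over time. This matters most for BIS. The plan intends both arms to be at the same depth of anesthesia, and the BIS series is the evidence for that. It calls for a between-flow comparison over time on as many patients as possible.

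**Working it through.** **Inputs from the documents.** Two arms (1 and 4 L/min), seven variables, one reading every 5 minutes. The available text gives no operation lengths, sample size or number of readings, so the plan has no figure of its own to reproduce.

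**Assumed inputs.** Log-normal duration with median 90 min and CV 0.4; 60 patients, 30 per arm; readings per patient = floor(duration/5) + 1, which includes time zero; patient share of variance 0, 0.3 or 0.5, with AR(1) correlation 0.5, 0.7 or 0.9 in the rest.

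**Step 1: patients with a complete series.** σ = √ln(1 + 0.4²) = √ln 1.16 = 0.385. The share with a complete series to w minutes is 1 − Φ(ln(w/90)/σ).
- 60 min: ln(60/90)/0.385 = −1.05, so 85%.
- 90 min: 0, so 50%.
- 120 min: ln(120/90)/0.385 = 0.75, so 23%.

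With median 60 min the shares are 50%, 15% and 4%. With median 120 min they are 96%, 77% and 50%. The window that keeps everyone ends at the shortest operation: about 37 min and 8 readings, which uses about 40% of all readings.

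**Step 2: a workable window.** Take the latest reading reached by at least 75% of patients (at least 45 of 60). In simulation this has a median of 15 readings (5th to 95th percentile 13 to 16), so it ends at about (15 − 1) × 5 = 70 min. A mixed model in this window uses about 70% of all readings.

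**Step 3: precision.** The ratio below is the standard error of the window-average group difference from complete series, divided by that from all available readings in the same window. It comes from generalised least squares with categorical time by arm. The range covers the correlation grid.

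| Window | Complete series | SE ratio |
|---|---|---|
| 60 min | 85% | 1.075 to 1.086 |
| 75% rule (about 70 min) | at least 75% | 1.12 to 1.14 |
| 90 min | 50% | 1.342 to 1.423 |
| 115 min | 26% | 1.687 to 2.008 |

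As a rough check on the second row, if exactly 75% were complete and the other patients were worth as much as complete ones, the ratio would be √(1/0.75) = 1.155. The simulated values lie just below that.

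**Step 4: the missing term.** Suppose the arm means at time t are μ + δ(t) and μ − δ(t), with equal arm sizes. Their average is μ at every t, so the time effect is zero although the courses differ by 2δ(t). A t, Welch or Mann-Whitney test compares the arms on one value per patient, such as one time point. It does not test whether the courses differ. Only a group-by-time term does.

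**The case against.** Much of the opposing case stands.

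- **Unseen text.** The part of Material and Methods that was unavailable may fix the analysed times or the type of operation. The SAP's reference to different periods is also compatible with a few selected times, where the loss is smaller. This makes the unequal-length argument conditional. It does not put a group-by-time term into the SAP sentence, though the authors may intend a group factor.
- **A large loss of precision.** A reader might infer from the table that the plan costs 34% to 101% in standard error. The documents do not support that. Those figures belong to 90 and 115 min windows that only 50% and 26% of patients reach under the assumed durations, and the plan does not choose such a window.
- **Inflated type I error.** A reader might also infer this. With AR(1) correlation and no sphericity correction, the simulated error of the time test is 7.5% to 10.0% at 8 readings. The plan does not say that correction will be omitted, and with Greenhouse-Geisser the error at 8 readings is 4.5% to 5.0%. The point does not rest on it.
- **Secondary data.** The aim is oxidant/antioxidant balance. TAS, TOS, albumin and CRP are drawn before, during and after the operation, so the open-ended-series problem does not arise for them.
- **The mixed model has limits.** It too stops at a window. Readings after surgery do not exist rather than being missing, and the model must assume that stopping is ignorable. Its error rate was not simulated here, and the precision check treats the covariance as known and ignores baseline adjustment. A non-significant group-by-time test would not show equal depth of anesthesia.

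**Conclusion.** The point holds as a minor, inexpensive improvement. For the 5-minute series, repeated measures ANOVA fits operations of unequal length poorly, and the sentence as written does not test whether the 1 L/min and 4 L/min courses differ. The second part needs no numerical assumption. The first depends on there being no fixed analysed times in the unavailable text.

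In a sensible window the standard error is about 12% to 14% wider than it need be, given the assumed durations, sample size and correlations. Fixing the window in advance also removes a choice that could otherwise follow the data. None of this shows a fault in the analysis of the oxidant/antioxidant outcome.

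**What to change.** For the 5-minute series only, add to the Statistical Analysis Plan:

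> HR, SpO2, SBP, DBP, ETCO2, temperature and BIS will be analysed by a linear mixed model with group, time (categorical), group-by-time and the baseline value, using all available readings up to the latest 5-minute reading reached by at least 75% of patients (arms pooled, set from operation times alone before monitoring values are examined), with AR(1) residuals plus a patient effect, or AR(1) alone if that model does not converge, and Satterthwaite degrees of freedom. Group differences will be reported with 95% confidence intervals, together with the group-by-time test; a non-significant result will not be read as proof of equal depth of anesthesia. The model assumes that the end of the operation is ignorable given the observed readings.

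If the protocol already fixes a last reading or the analysed times, use those in place of the 75% rule. This change leaves the analysis of TAS, TOS, albumin and CRP as it is.

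**Cost.** SAP wording and a mixed-model procedure in the analysis software; no new data. The downsides are that readings after the window are not modelled, late estimates rest on fewer patients, and one covariance form may not suit all seven variables.
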